#### Follow-Up Phone Calls

The follow-up phone calls will be scheduled for 2 week and 6 weeks after the initial baseline data collection. Participants will be notified of these surveys through the mode of communication they indicated at baseline. If they indicated a preference for online surveys, they will be sent a link to the surveys. If they elected to complete them by phone, the participant will be contacted by a member of the research team to complete follow-up surveys. Similar to the baseline data collection, they survey may be completed online or administered by the research assistant over the phone. The two-week follow-up surveys will be identical to the baseline surveys.

The 6-week follow-up survey will be completed in the same fashion as the two-week survey. It will contain the same measures as the 2-week survey including that patient usability of the app will be assessed using the 18-item mHealth App Usability Questionnaire (MAUQ). Patient acceptability will be measured using the 20-item User Burden Scale. Additionally, participants will be invited to complete semi-structured interviews about their use experience to be completed at a later date and will be prompted to provide their preferred contact information for scheduling that interview.

#### The Use of BBN

Usage of the app is entirely self-paced. While some features do have recommended intervals for use (e.g., weekly writing), users are able to schedule these at any interval they choose. The app will be introduced to the participant by the behavioral health provider using a shared decision-making framework where providers and participants collaborate to discuss how to best use the application. The app will only capture data pertaining to utilization, which will include initial login date, last use date, number of logins, and number of times each component is accessed.

#### Focus Group and Semi-Structured Interviews for Aim 2

[name] and her research assistants will conduct semi-structured with BHPs, Clinical Staff, Providers and Administration and individual video or semi-structures phone interviews with patients. They will ask questions to BHPs, Clinical Staff, Providers and Administration and patients about feasibility, acceptability, and usability of BBN and overall clinical protocol. The BHPs will complete a 5-item questionnaire about their comfort-level with integrating mental health apps into clinic care.

The semi-structured interviews with BHPs, Clinical Staff, Providers and Administration will be guided by the

Tailored Implementation for Chronic Diseases Checklist (Flottrop, 2013). The interviews will occur in a private location at the clinic or via Zoom, be audio recorded, and last no longer than 1 hour. Specifically, the BHPs, Clinical staff, providers and administration will be asked about the Implementation Topics derived from the guideline checklist which includes: Recommendations, Individual and Health professional factors. Professional behaviors, Patient Factors, Professional Interactions, Incentives and Resources, Capacity for Organizational Change, Social, Political, and Legal Factors which relate to the feasibility and implementation efforts of mobile app integration within the clinical setting. The interviews will be audio-recorded and transcribed.

The semi-structured interviews with patients will be guided by the Integrated Promoting Action on Research Implementation in Health Services framework. The interviews will occur in a private location at the clinic or via Zoom, be audio recorded, and last no longer than 1 hour. Specifically, with the patient interviews, patients will be asked about the following: 1) the overall usability of BBN, 2) the overall acceptability of BBN, 3) each major components of BBN, 4) the feasibility of incorporating BBN into the clinical practice, 5) the ease of using BBN to complete the surveys, and 6) strengths and

weaknesses of BBN for treatment of their mental health condition. The focus group and interviews will be audio-recorded and transcribed.

#### **Data Analysis**

Qualitative data will be tabulated and summarized using frequencies and percentages and will be analyzed using a direct content analysis approach. Focus group data will be transcribed and uploaded to QSR NVivo 12. As for qualitative data, a linear mixed effect model will be fitted to analyze each continuous outcome measured at different time points to estimate the potential intervention effect size for the future design of larger trials. A generalized linear mixed effect model with cumulative logistic link will be fitted to analyze ordinal outcome. Analysis will be performed using SAS.

#### **EHR/Clinical Notes Data Collection:**

In addition, we will collect basic demographic and clinical information about the patient by abstracting information from the clinical notes and E.H.R. The information will be abstracted by the BHP who will participate in the study. The information collected will be: race/ethnicity, age, gender, health insurance status, educational level, employment status, physical health conditions, BMI, and mental health diagnoses. The information will be saved in the Excel file with unique patient study IDs.

#### **Data Storage:**

The patient data for Aim 2 will be kept electronically in the project folder in the College of Nursing server, which will be password protected. The patient database will only contain the study IDs. BBN usage data will be downloaded by [name] PhD through an online portal to which he only has access. This portal does not contain identifiers and linkages will occur through download dates and times. [name] PhD will share this via a secure shared drive to which only the research team will have access. Nebraska Medicine BHPs, who have ethical access to patients, will keep a list of patient names and the study ID electronically in a password protected folder.

#### **Measurement:**

All assessments will be scored using tools validated

#### **Standard Clinical Assessment for Patients:**

- Patient Health Questionnaire 9 items (PHQ-9): Baseline and two follow-up visits
  - The PHQ-9 is an assessment tool validated for provisional diagnosis and grading symptom severity of Major Depressive Disorder.
- 7-item Generalized Anxiety Disorder Scale (GAD-7): Baseline and two follow-up visits
  - GAD-7 screens for Generalized Anxiety Disorder and assesses severity.

#### **Research Assessment for Patients**

- Trauma History Questionnaire
  - The Trauma History Questionnaire (THQ) is a 24-item self-report measure that examines experiences with potentially traumatic events such as crime,

general disaster, and sexual and physical assault using a yes/no format. For each event endorsed, respondents are asked to provide the frequency of the event as well as their age at the time of the event. The THQ can be used in both clinical and research settings, and is available in English. Will be assessed at Baseline

- Promis-Emotional Distress Depression Short Form 8a
  - is an 8 item self-report measure and this is not a diagnostic screening., Baseline and follow-ups
- Post-Traumatic Stress Disorder Checklist for DSM-5 (PCL-5): Baseline and two follow-up visits
  - 20 item report assesses for the 20 DSM-5 symptoms of PTSD.
- Pittsburgh Sleep Quality Index: Baseline and two follow-up visits
  - 19 questions rated by the participant and 5 by a bed partner (if available). Used to assess sleep quality and broken down into 7 components.
- mHealth App Usability Questionnaire (MAUQ): After the 2nd visit
  - A reliable and validated tool assessing the usability of mHealth apps. Will be used to evaluate BounceBack Now
- User Burden Scale: After the 2nd visit
  - Evaluates the difficulty of use and burden the app may place on participants.

Research Assessment for BHP

- Self-Management Support in Behavioral Health Organizational Assessment Tool (SMS): Baseline
  - Designed to assist behavioral health organizations in delivering self-management support to clients managing serious mental illness.

**Addressing Needs of African American and Low-Income Patients**

The participating clinics Fontenelle, Downtown, Midtown and Bluestem Health Clinics primarily serve African American or low-income patients. Thus, almost all of the patients who will be recruited for Aims 1 and 2 are expected to come from these two population groups. Race/ethnicity and income information will be collected through E.H.R. data. The needs of these two patient population groups will be met by recruiting the patients primarily from these two population groups for Aim 1 to ensure that their perspectives will be reflected in the patient education materials. Similarly, the needs of these patients' groups will be met by conducting a pilot for Aim 2 and obtaining feedback through the individual interviews we conduct at the end of the study.

**C. Select any of the following that apply to the research:**

Phase I study

Randomization

Placebo (or non-treatment arm)

Washout

Sensitive surveys or questionnaires

- ♦ None of the above

**D. Identify:**

**1. All procedures, interventions, evaluations and tests performed solely for research purposes (eg, administration of an investigational drug or a new psychological assessment instrument; randomization)**

BBN is being used for the purposes of research.

The focus groups conducted for Aim 1 are for the purpose of research.

We will ask the patients to complete the following instruments for the purpose of research for Aim 2:

- THQ
- Promis 8a
- Pittsburgh Sleep Quality Index
- PCL-5
- MAUQ
- User Burden Scale

We will ask the BHP to complete Self-Management Support in Behavioral Health Organizational Assessment Tool (SMS) and a 5-item comfort level questionnaire.

**2. All procedures, interventions, evaluations and tests performed for clinical indication but more frequently than they would be if the subject was not participating in the research (eg, extra blood tests; additional radiology exams)**

Not Applied.

**E. Describe briefly the statistical methods used to analyze the data (or reference the appropriate section of the detailed protocol or grant).**

Aim 1:Qualitative data will be analyzed using a directed content analysis approach.

Peer debriefing and member checking will be utilized to validate the data.

Aim 2:Quantitative data regarding usability, acceptability and feasibility will be tabulated and summarized using frequencies and percentages. Qualitative data will be analyzed using a directed content analysis approach. Interviews will be transcribed verbatim and uploaded to QSR NVivo 12. Data will be validated through the process of peer debriefing and thick description. Additionally, for usability, acceptability, and feasibility, both quantitative and qualitative data will be integrated and analyzed collectively. A linear mixed effect model (LMM) will be fitted to analyze each continuous outcome measured at different time points

to estimate the potential intervention effect size for future design of larger clinical trial. Transformation of continuous outcome will be performed as needed to satisfy distribution assumption. A generalized linear mixed effect model (GLMM) with cumulative logistic link will be fitted to analyze ordinal outcome. Analysis will be performed using SAS version 9.4 (SAS Institute, Cary, NC).

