## **CHARACTERISTICS OF THE SUBJECT POPULATION**

### **4. Accrual**

**A. Is this study conducted solely at sites under the oversight of the UNMC IRB (e.g. UNMC, Nebraska Medicine, CHMC, UNO)?**

Yes

**1. How many subjects will need to be consented (per group, as applicable) in order to achieve the scientific objectives of the research?**

Aim 1: Total 14 - 10 patients and 4 behavioral health providers

Aim 2: Total 45 - Patients (15), BHPs (10), Clinical staff, providers and administration (20)

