**2. What is the statistical or other justification for the total number of subjects described above?**

Because of the pilot nature of the study, it is not anticipated that quantitative results will achieve statistical significance. The data will primarily serve to demonstrate feasibility of our approach and success recruitment for a larger clinical trial. We aim for the number indicated in Section II 4 A 1, based on our ability to recruit patients at the clinic during the pilot funding period.

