**1.) Baseline**

Prior to engagement with the BBN application and as part of standard care at the clinic, a primary care provider at one of the specified Fontenelle, Downtown, Midtown or Bluestem Clinic locations will do a standard "warm handoff" referral to a behavioral health provider (BHP) if the patient is determined to have a behavioral health issue. All participants under Aim 2 will have gone through this process and have discussed identified mental health needs with both the BHP and their primary care provider. They will therefore already be receiving behavioral health services. In this context, BHPs will advertise BBN and the study to participants they believe may benefit, which mimics naturalistic app recommendations in this setting. For such patients, the BHP will provide the patient with a QR code that directs participants to where they can download BBN, which is publicly available. Continuing further with standard care when using apps, BHPs will have discretion as to whom they will recommend BBN. All BHPs have been trained in its use and have viewed its functionality. They will then guide patients through the sections that they perceive as relevant for that patient. Any patient may be directed through these procedures regardless of whether they elect to participate in the research phase. Thus, all Aim 2 procedures to this point are for standard of care. However, they must have had BBN recommended to them by the BHP in order to be eligible for Aim 2 research. For any adult participants (i.e., 19+ years of age) to whom they introduce BBN, BHPs will be asked to advertise a research study on the use, perceptions and initial effectiveness of BBN. To do so, they will use flyers with a QR code that links to a Redcap survey. The BHP will inform the patient that participation in the

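### The mixed model is said to estimate the intervention effect size, but Aim 2 has no comparison group, so it can give only uncontrolled within-person change

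*Combined protocol and SAP*

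**What the plan says.** The target of the quantitative analysis is stated twice. Item 12.E (statistical methods) fits a linear mixed model to each continuous outcome measured over time "to estimate the potential intervention effect size for future design of larger clinical trial". The Data Analysis paragraph of item 12.B gives the purpose as "to estimate the potential intervention effect size for the future design of larger trials". Neither place names the contrast, the model terms or any limit on interpretation.

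The design is described elsewhere:

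- **Patients.** Item 4.A.1 gives 15 patients for Aim 2, with no arms. The other Aim 2 subjects are providers, staff and administrators.
- **Comparison.** Item 12.C offers randomization and a placebo or non-treatment arm as options. The one marked is "None of the above". No historical or concurrent comparison group is described anywhere.
- **Exposure.** For patients recruited by a behavioral health provider (BHP), the Baseline text says "they must have had BBN recommended to them by the BHP in order to be eligible for Aim 2 research". Opt-in patients complete baseline first, and their BHP brings the app into later appointments.
- **Other care.** Of Aim 2 patients the Baseline text says "They will therefore already be receiving behavioral health services". The text that follows has them keep meeting their BHP as usual.
- **Timing.** There is one baseline, with follow-up 2 and 6 weeks later (Follow-Up Phone Calls).

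The nearest caveat is in item 4.A.2: "it is not anticipated that quantitative results will achieve statistical significance", and "The data will primarily serve to demonstrate feasibility of our approach".

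**The concern.** An intervention effect is a difference between what happens with the intervention and what would have happened without it. Aim 2 observes only the first. A mixed model fitted over time in a single group estimates change over time, whatever that change is called.

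There are specific reasons to expect change without BBN. Patients enter after referral for an identified behavioral health problem, so scores may fall by regression to the mean or natural course. They are also receiving care that may itself help.

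What is at stake is how the pilot's main quantitative result is described and carried forward. Under the present wording, a before-after change can be reported as the size of the BBN effect, and both statements direct it to the design of the next trial. The Baseline text adds to this reading by having BHPs advertise the study as one that covers BBN's initial effectiveness.

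**Working it through.** The plan gives no SD, expected change, target difference, alpha or power, so there is no figure to reproduce. The check is on what the model can estimate, followed by an illustration.

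**Step 1. What the model estimates.** The plan does not list model terms. The assumption here is a fixed effect for visit (baseline, 2 weeks, 6 weeks) and a patient random effect. The coefficient for a follow-up visit is then the mean change from study baseline, C. Write

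C = E + U

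- E is the effect of adding BBN to usual care.
- U is the change that would have occurred over the same weeks under usual care without BBN (concurrent care, natural course, regression to the mean).

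A two-arm trial estimates E, because the control arm supplies U. Aim 2 supplies C alone: one equation, two unknowns.

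**Step 2. Whether either recruitment route supplies U.** BHP-route patients have had BBN recommended. Opt-in patients receive it in later appointments, but the plan sets out no unexposed follow-up period for them and no between-route contrast. Neither route forms a comparison group.

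**Step 3. Whether the caveat in item 4.A.2 covers this.** It concerns significance, which is a matter of precision. With 15 complete patients, the 95% CI half-width for a simple mean change is t(0.975, 14)/√15 = 2.145/3.873 = 0.55 SD of change. More patients would narrow that interval, but it would still be an interval for E + U.

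**Step 4. Illustration of the consequence (all inputs assumed, in outcome SD units).** Suppose C = 0.5 and a later two-arm trial takes it as the between-arm effect, with a two-sided 5% test and 80% power. The normal approximation is

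n per arm = 2(1.960 + 0.842)²/d² = 15.70/d²

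It gives 62.8 at d = 0.5, 174.4 at d = 0.3 and 32.0 at d = 0.7. The exact two-sample t calculation gives 63.8, 175.4 and 33.02, rounded up in the table.

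| Assumed U | E = 0.5 − U | Power with 64 per arm | Needed per arm |
|---|---|---|---|
| 0 | 0.5 | 80% | 64 |
| 0.2 improvement | 0.3 | 39% | 176 |
| 0.2 worsening | 0.7 | 98% | 34 |

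All three rows are compatible with the same observed change of 0.5, and the pilot has no data to tell them apart.

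**The case against.** The strongest reply is that this is a feasibility pilot and says so. The abstract speaks of feasibility and acceptability, the objectives contain no efficacy aim, item 4.A.2 does not expect significance, and item 12.C shows openly that there is no control. Item 12.E asks only for a brief description. The word potential hedges the claim, and a standardized before-after change is often called an effect size. Much of this stands. It limits the weight of the point, and it means that neither the design nor the model needs to change. It does not answer the point, because none of these statements says that the estimated change cannot be attributed to BBN.

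A reader might infer more than the documents support:

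- **That the pilot figure will be used directly to size the next trial.** The documents say only that it is estimated for that trial's design. The sample sizes above show why the limit should be stated. They do not predict what the sponsor will do.
- **That every patient had BBN recommended before entering.** The eligibility sentence sits under the BHP route. In the opt-in route, baseline comes before the app is brought into care. The absence of a comparison group rests on items 4.A.1 and 12.C and does not need this claim.
- **That flyers or consent forms carry an effectiveness claim.** Their text is not available here. Only the phrase in the Baseline text can be assessed.

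Baseline timing relative to the start of BBN differs between the two routes. That is a separate issue, which relabeling does not resolve, and it should be raised on its own.

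**Conclusion.** The point holds as a mislabeled quantity. The plan says it will estimate an intervention effect size. The design can deliver only mean within-person change under BBN plus usual behavioral health care, and no section states that limit. This conclusion follows from the single-group design and does not depend on any assumed number.

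Its size in this trial cannot be computed. The error may run in either direction, and the illustration (64 per arm planned against 176 or 34 needed) rests wholly on the assumed 0.5 SD change and ±0.2 SD change without BBN.

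This is a wording correction that should be made. It is not a reason to add a control arm or drop the mixed model. The model's outcome variance and within-person correlation remain useful for planning, though imprecise with 15 patients.

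**What to change.** In item 12.E and in the Data Analysis paragraph of item 12.B, replace the stated purpose of the mixed model with:

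> to estimate mean within-person change from study baseline to 2 and 6 weeks under BBN plus usual behavioral health care, with 95% CI; because there is no comparison group, this is not an estimate of the BBN effect and will not by itself be taken as the between-arm effect for a larger trial

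Bring the effectiveness wording in the Baseline text of item 12.B into line with this. Optionally, add that the outcome variance and within-person correlation will be reported for planning, with a note on their imprecision at 15 patients.

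The cost is a minor text amendment in three places, with no added patients, visits or measures and no change of model. The sponsor gives up an effect-size claim that the design cannot support.

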**F. Does this study involve the collection of blood, urine, saliva or other human biological material (HBM)?**

No

**DRUGS, BIOLOGIC DRUGS AND DEVICES**

**13. Drugs and Biologic Drugs**

**1. Does this research involve the use of drugs or biologics?**

No

**14. Devices**

**1. Does this research involve a medical device(s)?**

Yes

**A. Are any of the medical devices used in this study FDA approved?**

No

**B. Are any of the medical devices used in this study not approved by the FDA?**

Yes

**(i) Describe the device(s)**

BBN is a trauma-focused technology tool to enhance equity and outcomes of trauma-related disorders in primary care settings. BBN is a self-help, trauma-focused mental health guide with automated assessment with treatment guidance and in-app guidance through evidence-based treatments for depression, PTSD, sleep difficulties, and anxiety.

**(ii) Specify the sponsor of the device(s)**

The research team is the sponsor of the device. The app is copyrighted under MUSC (primary) and UNL (secondary). The app is publicly available and free. The app is available to anybody who is interested in using.

**(iii) Do any of the devices have an IDE number?**

No

**(iv) Are any of the device(s) a Non-significant Risk Device (NSRD)?**

Yes

**a. Provide rationale.**

Under 21 CFR 812.3(m), a Significant Risk device is defined as an investigational device that:

1. Is intended as an implant and presents a potential for serious risk to the health, safety, or welfare of a subject;
2. Is purported or represented to be for use supporting or sustaining human life and presents a potential for serious risk to the health, safety, or welfare of a subject;
3. Is for a use of substantial importance in diagnosing, curing, mitigating, or treating disease, or otherwise preventing impairment of human health and presents a potential for serious risk to the health, safety, or welfare of a subject; or
4. Otherwise presents a potential for serious risk to the health, safety, or welfare of a subject.

